Inclusion. Participants will be JVS service-seeking adults who are unemployed, score at least five on the MINI-SPIN (Connor et al., 2001), meet structured interview criteria for SocAD. Participants taking psychotropic medications will be offered participation without restriction. We will monitor medication as a potential moderator of outcomes. Participants must agree to refrain from outside psychotherapy throughout the active 4-week treatment period.

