Measures of employment. Several methods are in place to assess employment including: a) Following Vinokur et al.'s JOBS program, our primary work-related outcome measures will be the reported number of paid work hours per week during the follow-up period.; b) In the R34, participants were asked to recall the average number of hours worked per week over three months: this yielded little variance, with many respondents reporting either 0 or 20 hours per week. This clustering is likely related to difficulty recalling work hours over a three-month period, especially with inconsistent schedules or more than one employer. Precision on 'number of paid hours' will be enhanced by a new "timecard" system wherein gift cards are remotely "recharged" with a \$5 incentive for every pre-dated, weekly "timecard" that is returned by mail or text within one week of the due date. These timecards will include questions on the hours worked per day and number of missed work days as a measure of work impairment; c) Measures of work status and time to re-employment will be collected at follow-up using a modified version of a Work Activity Questionnaire used by Vinokur (15). This questionnaire also inquires about the number of job interviews and job applications completed during the follow-up period; e) Job search self-efficacy and motivation will be measured using Vinokur et al.'s Job Search Motivation Index (15, 46), which assesses job search self-efficacy, attitude, subjective norms, and intention to engage in intensive job search; f) Finally, work productivity and performance will be measured by the work performance subscale of the Multidimensional Scale of Independent Functioning (MSIF) (96). This instrument has good criterion, discriminant, interrater and construct validity along with strong inter-rater reliability (96). Convergence of the multiple methods of assessing paid work hours will be examined using confirmatory factor analysis, and missing data for each method will be examined for systematic patterns. If adequate convergence is found, multiple methods may be analyzed as observed indicators of a latent "paid work hours" construct; advantages include reduction in method-related error variance, strategies for analysis of construct- and

method-specific effects, and accommodation of missing data on one or more measures. A latent variable approach is expected to be especially informative for Aim 2, which examines mediators of WCBT effects on work outcomes.

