Measures of client functioning. Overall disability will be measured using the Sheehan Disability Scale (SDS) (Sheehan, 1996). The SDS is a commonly used three item measure of functional impairment and has high internal consistency and construct validity (Leon et al., 1997).

Measures of other symptoms in subjects. Since general anxiety and depression may influence outcomes, we will assess comorbid depressive symptoms using the PHQ-9, which has adequate reliability and validity (101), and anxiety symptoms using the Brief Symptom Inventory-18 (BSI-18) which has well-established reliability and validity (102).

Demographics. Collected demographic information will include gender, date of birth, race/ethnicity, education level, family composition, and other relevant clinical and demographic characteristics. Given the impact of the number of care-given children, ages of children, health problems among children, and prior work experience on the welfare status in our Women's Employment Study, we will also collect this information from participants.

Measures of treatment credibility and beliefs. Treatment expectations will be measured using the Expectancy Rating (Borkovec & Nau, 1972). This is a four item self-report instrument designed to assess patient expectations regarding change with treatment. The Expectancy rating will be administered before treatment and then after the 3rd WCBT session such that subjects can report expectations after the subject has been well socialized to the treatment. The Expectancy Rating has high internal consistency and high test-retest reliability (Devilly et al., 2000). Treatment satisfaction will be rated using the Treatment Impressions Rating Scale, a Likert-based self-report instrument.

VAU active phase questionnaires. Participants in the VAU (control) condition will complete measures at time intervals consist with session measures completed by the WCBT intervention condition. These questionnaires include a series of sham measures are not sensitive and do not relate to study outcomes (e.g., health; physical activity; sleep) as well as a measure of social anxiety symptom (Mini-SPIN) and medication use and adherence (Morisky). VAU participants will have the option of receiving a link to complete these measures via an electronic data collection system (qualtrics) or receiving paper copies of the questionnaires at baseline that can be returned by mail following the twice weekly administration schedule.

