Other treatments. Measures of other treatments include: a) The Morisky Adherence Measure (107) is a 4-item self-report measure of medication adherence, with high internal consistency and concurrent and predictive reliability when applied to medication use (107). We will monitor medication throughout treatment and follow-up; b) We will track the specific number and type of JVS services utilized, according to computerized records of client service use at both JVSD and JVSLA; c) The CBT Use Questionnaire tracks self-use of CBT and use of additional therapist-directed CBT, over the follow-up period, as utilized in the R34 study.

Table 4. Measure Administration Schedule

Measure and Reference	Abbreviation	Time points for Measurement	Measure Type and Person Completing Assessment
MINI-SPIN Social Phobia Inventory (Connor et al., 2001)	MINI-SPIN	Screening, Sessions 1,3,5,7	Subject-Report Questionnaire
MINI International Neuropsychiatric Interview v. 7.0 (Sheehan et al., 2015)	MINI	BL, PT, 12 wk, 26 wk, 52 wk.	Diagnostic Interview
Baseline Demographic and Work History	NA	BL	Clinician Administered Questionnaire
Brief Psychiatric Rating Scale (Ventura et al., 2003)	BPRS)	BL, PT, 12wk, 26wk, 52 wk	Clinician Rating Scale/Interview
Liebowitz Social Anxiety Scale (Liebowitz, 1987)	LSAS	BL, PT., 12 wk, 26 wk, 52 wk	Subject-Report Questionnaire
Alcohol, Smoking and Substance Involvement Screening Test	ASSIST	BL, PT., 12 wk, 26 wk, 52 wk	Clinician-Administered Questionnaire
Sheehan Disability Scale (Sheehan et al., 1996)	SDS	BL, PT, , 12 wk, 26 wk, 52 wk	Subject-Report Questionnaire
Social Phobia Inventory	SPIN	BL, PT, 12 wk, 26 wk, 52 wk	Subject-Report Questionnaire
Interpersonal Competence Questionnaire	ICQ	BL, PT, 12 wk, 26 wk, 52 wk	Subject-Report Questionnaire
Brief Symptom Inventory-18	BSI-18	BL, PT, 12wk, 26 wk,	Subject-Report Questionnaire

		52 wk	
Follow-Up Questionnaire Employment	FUQ-E	12 wk, 26 wk, 52 wk	Subject-Report Questionnaire
Multidimensional Scale of Independent Functioning – Work Performance Anchors	MSIF	PT, 12 wk, 26 wk, 52 wk	Clinical Administered Interview
Job Search Behavior Questionnaire	JSB	BL, PT, 12 wk, 26 wk, 52 wk	Subject-Report Questionnaire
Brief Comprehensive Effects of Alcohol Questionnaire	B-CEQA	BL, PT, 12 wk, 26 wk, 52 wk	Subject-Report Questionnaire
Drinking Motives Questionnaire	DMQ	BL, PT, 12 wk, 26 wk, 52 wk	Subject-Report Questionnaire
Flexibility Measure	AAQI	BL, PT, 12 wk, 26 wk, 52 wk	Subject-Report Questionnaire

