We will use the same MLM approach that we used in our R34 pilot to compare individuals assigned to WCBT vs. VAU. 3-level models will incorporate repeated measures on individuals nested within the 50 6-person groups randomly assigned to WCBT or VAU. HLM software will be used (115). Individual baseline scores on each outcome variable will be incorporated as level 2 covariates to increase the precision and statistical power of tests of the randomized intervention and reduce regression to the mean artifacts (116). Observations will be centered at a post-intervention or follow-up time point to provide a straightforward WCBT vs. VAU comparison on outcome level. Persistence of intervention effects will be assessed through WCBT vs. VAU comparisons on the level 2 slopes characterizing individual outcome trajectories through 52-week follow-up; quadratic or piecewise slope terms (117) will be included if needed to reflect acceleration or slowing of change over time. Power estimates for the planned MLM analyses were conducted using Optimal Design software (118). The entire sample of 300 individuals, nested within 50 groups, with 5 assessments over time, will provide power of .8 to detect (at 2-tailed $p < .05$) an intervention effect on intercept or slope of at least $d=0.34$; power estimates range from .7 to detect $d=.30$ to .9 to detect $d=.39$. Effect sizes in the R34 pilot ranged from .46 for hours worked to 1.36 for social avoidance; this suggests that power in this larger R01 will be adequate to detect condition differences on all outcomes, including employment. These estimates assume a minimum intraclass correlation (ICC) between groups of .01, which is larger than the ICCs observed in the R34 pilot. If the ICC for the R01 is found to be substantially higher at .03, the effect size detectable with power of .8 will rise only slightly, from $d= .34$ to $d=.36$.

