Aim 2. Evaluate whether improvements in social anxiety mediate the effect of WCBT upon employment related behaviors and outcomes. We hypothesize that reductions in social anxiety will lead to more employment related behaviors and greater employment success. In addition, it is hypothesized that specific reductions in social anxiety will better explain the effects of WCBT on employment compared with general improvements in depression and generalized anxiety. Multilevel SEM will assess whether reductions in social anxiety explain WCBT effects on subsequent employment (hours worked, job search activities, job search self-efficacy). This approach provides several advantages that are essential to testing mediation in this design. First, it accounts for nesting of individuals within randomized groups (119); it allows us to focus on change by using centering to disentangle between- and within-person effects (112); it lets us specify temporal order (i.e., change in social anxiety symptoms precedes change in employment related outcomes), and it accommodates latent variables (e.g., hours worked) (119). In addition, multilevel SEM provides ways to formally compare multiple alternative mediation paths (120), which will be essential to testing our hypothesis that reduction in social anxiety will better explain WCBT effects on employment than improvements in depression and generalized anxiety. Mplus software (121) will be used for these analyses due to its flexible estimation capabilities, use of bootstrap algorithms appropriate for testing indirect effects (122), and ability to test and compare specific mediation effects (123). Simulations conducted in MPlus and ProcClin (124) indicate that power can be expected to exceed .8 to detect significance at $p < .05$ an indirect effect in which the two component standardized direct effects a' (WCBT \rightarrow SocAD) and B' (SocAD \rightarrow employment-related outcome) are .20 or above, which is larger than the minimum a' and B' effects observed in the R34 pilot.

Aim 3. Explore moderators of the effects of WCBT, including site, race/ethnicity, education, prior work experience, psychiatric medication status and comorbid depression. Moderation will be tested by adding moderating variables to the MLM regression models testing mental health and employment outcome effects (Aim 1). Because groups are nested within site (16 sites at JVSD and 34 at JVSLA),

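### For paid work hours, MSIF and FUQ-E outcomes, the Aim 1 baseline-score adjustment has little or nothing to adjust for, and no other prognostic covariate is prespecified

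*Combined protocol and SAP*

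**What the plan says.** - **Aim 1 (Power Analysis and Statistical Strategy)** fits three-level models and specifies one kind of adjustment: "Individual baseline scores on each outcome variable will be incorporated as level 2 covariates to increase the precision and statistical power". No other covariate is named there.
- **Measures of employment** sets the work outcome: "our primary work-related outcome measures will be the reported number of paid work hours per week during the follow-up period".
- **Inclusion**: "Participants will be JVS service-seeking adults who are unemployed". No hours threshold or recall window defines the term.
- **Table 4** schedules "Follow-Up Questionnaire Employment" (FUQ-E) at 12, 26 and 52 weeks, and the MSIF work anchors from post-treatment. Neither has a baseline. Job search behavior (JSB) and job search self-efficacy (JSSE) do. "Baseline Demographic and Work History" is taken at baseline.
- **Demographics** adds education and prior work experience to the baseline data.
- **Aim 3** gives those two variables their only named analytic role: "Explore moderators of the effects of WCBT, including site, race/ethnicity, education, prior work experience, psychiatric medication status and comorbid depression".
- **General approach to quantitative analysis** compares the arms on all baseline variables and says that those differing significantly will be considered as covariates. It also allows survival functions for censored variables.
- **Randomization** fixes 17 WCBT and 17 VAU groups at JVSLA, and 8 and 8 at JVSD.

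**The concern.** The baseline-score rule suits the symptom scales, where the earlier score usually predicts the later one. For paid hours it fails: the entry criterion removes most of the spread in the covariate, and the schedule does not list its measurement. An analyst who follows Aim 1 literally has nothing useful to enter for the primary work-related outcome, and must either fit the model unadjusted or choose covariates later.

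Two things are at stake. One is precision on the outcome that had the smallest pilot effect (.46 for hours, against up to 1.36 for social avoidance). The other is protection against a chance difference in employability between the arms when only 50 groups are randomized.

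**Working it through.** **Inputs from the documents.** 50 groups of 6 (J=50, n=6), 25 per arm; two-sided .05; ICC .01, with .03 as sensitivity. Stated results: power .8 at d=.34, .7 at d=.30, .9 at d=.39; detectable d .36 at ICC .03.

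**Input not in the documents.** R², the share of individual-level variance in hours explained by baseline predictors. It is assumed, over the range .05 to .20.

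**Formula.** Var(d) = 4·[ICC + (1−ICC)(1−R²)/n]/J, with a noncentral t on J−2 = 48 df. This compares the arms on outcome level and takes no credit for repeated measures.

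**Step 1: reproduce the plan's figure with R²=0.** Var = 4·(.01 + .99/6)/50 = 4·.175/50 = .0140, so SE = .1183. Power is .700 at d=.30, .804 at .34 and .898 at .39. Detectable d at power .80 is .338. At ICC .03, Var = 4·(.03 + .97/6)/50 = .01533 and detectable d is .354, against .36 stated. The plan's figures are matched closely with no covariate.

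**Step 2: add assumed covariates (ICC .01).**

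| Assumed R² | Var | SE | Detectable d (power .80) | Power at d=.34 | .0140/Var |
|---|---|---|---|---|---|
| 0 | .01400 | .1183 | .338 | .804 | 1.00 |
| .05 | .01334 | .1155 | .330 | .822 | 1.05 |
| .10 | .01268 | .1126 | .322 | .841 | 1.10 |
| .15 | .01202 | .1096 | .313 | .860 | 1.16 |
| .20 | .01136 | .1066 | .305 | .878 | 1.23 |

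The last column is the equivalent increase in the number of groups, and so in participants, at fixed group size: 5% to 23%. If the covariates also explained the same share of the between-group variance, the last detectable d would be .303 instead of .305.

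**Step 3: can the significance rule stand in for this?** Assume that the baseline predictor also has ICC .01 and is tested alone at .05.

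- The SE of a standardized baseline difference is .1183, so significance needs a difference above 2.011 × .1183 = .238 SD.
- A difference of .20 SD or more in either direction arises by chance about 9% of the time (.20/.1183 = 1.69).
- With R²=.10 the predictor correlates √.10 = .316 with hours, so an imbalance of .20 SD moves the hours contrast by .20 × .316 = .063 SD. That is .063/.34 = 19% of the design effect, and the rule would not be triggered.

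**Step 4: cost of the covariates.** The three person-level covariates draw on 300 people. A site term uses one group-level degree of freedom (48 to 47). At R²=.10 the detectable d stays at .322.

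**The case against.** The strongest reply is that little is at risk. The power statement lists no covariate gain among its assumptions and is reproduced without one. At the pilot effect for hours (d=.46), power is already .968 unadjusted. Every R² above is assumed, and at the low end (.05 to .10) power at d=.34 rises only 2 to 4 points. All of this stands. A reader might infer that the trial is underpowered for employment or that the sample size is wrong; the documents do not support that.

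A reader might also infer that hours get no adjustment at all and that any imbalance would go uncorrected. That is too strong, because the general approach can bring in work history or education after a significant baseline difference. But that route depends on the data and is optional, it misses moderate imbalances (step 3), and it is not a precision adjustment.

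Nor is the gap common to all employment outcomes. Aim 1 names hours worked, job search behavior and job search self-efficacy, and the last two have baseline scores.

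That baseline hours are zero for everyone is an inference. Unemployment is not defined in hours, the content of the baseline work history form is not shown, and Table 4 omits the weekly timecards, so it is not a full list of hours measurements. What can be said is that no baseline hours score is listed and that the entry criterion would leave it little variance.

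Finally, allocation is balanced by arm within site, so the documented between-site gap in education (40% against 5% with a bachelor's degree) is already balanced. Imbalance within site is not.

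**Conclusion.** The point holds in a limited form. For paid hours, MSIF and FUQ-E outcomes, the only prespecified Aim 1 covariate is either unlisted or nearly constant, so these outcomes have no effective prespecified prognostic adjustment. This is neither bias nor an error in the stated power. The loss is unused precision, some protection against chance imbalance, and an analyst choice left open on the primary work-related outcome.

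The size depends on an R² that the documents do not give. Over .05 to .20, detectable d would be .330 to .305 instead of .338. These figures assume a linear model; if hours need a transformation or another link, as the general approach allows, the gain would differ. The change is worth making because the data are already collected, but the trial's conclusions do not hinge on it.

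**What to change.** Amend Aim 1 before unblinding:

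1. State that the baseline-score covariate applies only to outcomes that Table 4 schedules at baseline.
2. For paid work hours, MSIF and FUQ-E outcomes, name prior work experience, education and baseline JSSE as level 2 covariates. Add site at level 3, because the number of groups per arm is fixed within site. Define how each covariate is coded.
3. For time to re-employment, use the same covariates in the survival model; the level 2 rule of the longitudinal model does not carry over directly.
4. Keep the significance-based rule, if wanted, for sensitivity analyses only.

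The cost is a few sentences and a few degrees of freedom in 300 people and 50 groups. No new data are needed, and the power statement can stay as it is.

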General approach to quantitative analysis. All raw data will be examined to verify quality and identify potential outliers and distributional issues that may require transformation or nonlinear link functions, including survival functions for variables subject to censoring (e.g., time to job loss). Psychometric properties of all measures will be verified in the study sample. Adequacy of randomization will be verified through multivariate comparisons of intervention and control arms on all baseline variables, using 2-level mixed effects regression models (individuals nested in groups). Variables showing significant baseline differences will be considered as covariates in subsequent analyses. Primary analyses will involve the ITT sample of all individuals who completed the baseline interview and were randomized. If there is sufficient variability in fidelity, participation, or drop-out, parallel secondary outcome analyses will incorporate measures of intervention dosage (i.e., attendance and participation) and fidelity as covariates, to account for variation in intervention engagement and retention. Additional analyses will identify characteristics of individuals who drop out or receive lower dosage. Covariates of treatment drop-out will be used to estimate complier average causal effects (126). Assessment attrition will be minimized through use of incentives and proactive retention strategies. In our pilot, our post-intervention retention rate was 86%; retention was equal across arms; no baseline variables were found to be related to attrition; and missing data patterns were not related to study outcomes. As in the pilot study, we will use pattern mixture modeling (127) to determine whether missing assessments at various time points affect study conclusions or are “ignorable” (i.e., conditionally missing at random). Missing data determined to be ignorable will be estimated using expectation maximization and multiple imputation procedures appropriate for longitudinal data (128). Sensitivity analysis will be used to examine the possible impact on study conclusions involving any missing data found to be nonignorable (129).

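### Aim 2 names no baseline covariates and no confounding sensitivity analysis for the social anxiety-to-employment path, which randomisation does not protect

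*Combined protocol and SAP*

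**What the plan says.** Under Power Analysis and Statistical Strategy, Aim 2 hypothesises that reductions in social anxiety lead to better employment outcomes and explain the WCBT effect better than general improvement in depression or generalised anxiety. The tool is multilevel SEM. Its stated advantages are that it handles nesting, separates between- and within-person effects by centring, accommodates latent variables, and that "it lets us specify temporal order (i.e., change in social anxiety symptoms precedes change in employment related outcomes". Aim 2 also plans a formal comparison of alternative mediation paths. On power it says that "power can be expected to exceed .8 to detect significance at $p < .05$ an indirect effect" when the two component paths "are .20 or above, which is larger than the minimum a' and B' effects observed in the R34 pilot".

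Covariates appear elsewhere. Aim 1 enters each person's baseline score on the outcome at level 2. The section on the general approach to quantitative analysis adds: "Variables showing significant baseline differences will be considered as covariates in subsequent analyses". That section's only sensitivity analysis concerns missing data.

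The Measures section says that depression and general anxiety may affect outcomes, and schedules the PHQ-9 and BSI-18 at baseline. Under Demographics it cites the bearing of children's number, ages and health, and of prior work experience, on welfare status, and says "we will also collect this information from participants".

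**The concern.** Cohorts are randomised, so the arms are comparable and the WCBT-to-anxiety path can be read causally. Within an arm nobody is randomised to a level of anxiety improvement. People who improve more may differ at baseline in work history, education, depression or family load, and those same features may affect how soon they work. Measuring anxiety before hours does not remove a cause that precedes both.

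The Aim 2 text names no covariate for this path, states no assumption of no confounding, and plans no check on one. At stake is the mechanism claim: that social anxiety, rather than something correlated with it, carries the employment effect. The design section gives mechanisms as a reason for choosing this design.

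**Working it through.** **Inputs from the plan.** "The entire sample of 300 individuals, nested within 50 groups, with 5 assessments over time" and "These estimates assume a minimum intraclass correlation (ICC) between groups of .01" (Aim 1 power paragraph). Both Aim 2 paths are .20, at p < .05. Sidedness is not stated for Aim 2; two-sided is assumed, as in Aim 1. **Not in the documents:** the strength c of a shared baseline cause, taken here as .1 to .4 on both variables. Anxiety is scored as improvement, so helpful paths are positive.

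**1. The plan's own power figure.** Joint significance of the two paths stands in for the planned bootstrap.
- Path a: SE = √((1 − .20²)/300) = .0566; z = .20/.0566 = 3.54; power Φ(3.54 − 1.96) = .942.
- Path b: SE = √((1 − .20²)/(300 × (1 − .20²))) = .0577; z = 3.46; power .934.
- Joint: .942 × .934 = .88. With design effect 1 + 5 × .01 = 1.05 on path a, .932 × .934 = .87. Simulation in 50 groups with cluster-robust errors gave .85.

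The stated power above .8 is reproduced. It takes the b path to be unconfounded.

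**2. A shared cause with no true b path.** Let one baseline cause, independent of arm, correlate c with the mediator and with the outcome. Then
- spurious b = c²/(1 − a²) = c²/.96;
- SE = √((1 − .96b²)/(300 × .96)).

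At c = .3: b = .09/.96 = .094, or 47% of the design value .20. SE = √(.9916/288) = .0587; z = 1.60; P(|Z| > 1.96) = .36. False mediation = .36 × .942 = .34.

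| c | spurious b | closed form | simulated, independent people | simulated, 50 groups, ICC .01 | same, cause adjusted for |
|---|---|---|---|---|---|
| .1 | .010 | .05 | .05 | .05 | .049 |
| .2 | .042 | .10 | .09 | .10 | .045 |
| .3 | .094 | .34 | .34 | .33 | .048 |
| .4 | .167 | .77 | .76 | .74 | .055 |

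The spurious path equals .20 when c = √(.20 × .96) = .44.

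**3. What modelling change achieves.** Longitudinal simulation, 1,500 trials per cell, true b = 0, strengths .3 / .4:

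| What the cause does | change scores | baseline scores as covariates |
|---|---|---|
| shifts stable levels only | .04 / .06 | .07 / .08 |
| shifts stable anxiety level, drives follow-up hours (baseline hours 0) | .04 / .05 | .09 / .20 |
| drives change in both | .40 / .80 | .53 / .93 |
| drives anxiety change and follow-up hours (baseline hours 0) | .33 / .73 | .40 / .79 |

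With the cause itself as a covariate, every cell lies between .04 and .07. Modelling change therefore deals with stable causes and fails when the cause drives change. For hours worked, the inclusion criteria make everyone unemployed at entry, so baseline hours should be about zero and carry almost no information about the cause.

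**4. The covariate rule.** A randomised comparison at the 5% level (assumed; the plan says only significant) flags a given balanced variable in about 1 trial in 20, however strongly it confounds path b. Site shows the mismatch. The Randomization section fixes 17 and 17 groupings at JVSLA and 8 and 8 at JVSD, so site is balanced by design and would not be selected. Yet the Study Sites section gives bachelor's degrees as 40% against 5%.

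**The case against.** A reader might infer that the path is adjusted for nothing, or that the plan rests on time order alone. The documents support neither.
- Centring is planned, and step 3 shows that modelling change can hold the error near 5% when the cause only shifts stable levels.
- Depression and generalised anxiety are competing mediators. If modelled jointly, they partly condition the anxiety path on mood.
- Temporal order is one advantage among several, and the text does not claim that it removes confounding.
- The imbalance rule is not the only mention of covariates. Aim 1 has baseline scores, and secondary analyses add dosage and fidelity.
- Aim 2 gives no model equation, so covariates are left unspecified rather than ruled out.

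All of this stands, but it does not close the gap. WCBT varies only between groups, so within-person centring need not protect an indirect effect of treatment. Mediators measured after baseline are not baseline adjustment and do nothing for work history, education, children or site. The baseline-score covariates are stated for Aim 1, and Aim 2 does not say that they carry over.

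**Conclusion.** The concern holds in this form: for the one non-randomised path in its mediation claim, Aim 2 specifies neither baseline covariates nor a confounding sensitivity analysis, and the protections it does list are partial. Job search activity and self-efficacy have baseline measures; hours worked has no useful one, so it is the most exposed.

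The size is conditional. About 34% false mediation at c = .3 and 76% at c = .4 come from a single-time-point model with one cause, a = .20 and equal same-direction associations. There is no inflation at .1, and opposite signs would mask mediation instead of creating it. A reader might infer that this trial will declare false mediation a third of the time. The documents do not support that: they give no confounder strengths, and the planned model is longitudinal and aimed at change. Nor does the point reach the randomised comparison in Aim 1.

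**What to change.** In both the mediator and the outcome equations of the Aim 2 model, prespecify a fixed set of baseline variables already collected: LSAS, PHQ-9, BSI-18, prior work experience, education, care-given children and site. Include them whether or not the arms differ on them. State the no-unmeasured-confounding assumption, and report how large a residual mediator-outcome correlation would have to be to reduce the indirect effect to zero.

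The cost is SAP wording, a few model terms and a few degrees of freedom. No new data are needed and Aim 1 does not change.
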